Target Population:	Adult patients with incurable (unresectable, non-ablatable-for-cure) confirmed hepatic primary (hepatocellular carcinoma or cholangiocarcinoma) or secondary (metastatic) tumour. All patients will have progressed or maintained stability on conventional chemotherapy. To be suitable, patients must have liver tumour(s) in the liver of size 1cm or greater, which are amenable to ultrasound-guided biopsy.
Objectives:	
PRIMARY OBJECTIVE:
 
To determine whether targeted release of doxorubicin from ThermoDox® ('drug') using mild hyperthermia generated non-invasively by focused ultrasound (FUS) is feasible in cancer patients.
 
SECONDARY OBJECTIVES:
 
 Part I only: To determine optimal FUS exposure parameters for a range of participant Body Mass Indices (BMIs) and tumour locations within the liver

	
 To assess the safety of FUS-induced mild hyperthermia for drug delivery To assess the local and systemic cytotoxic effects of ThermoDox® in this setting 
TERTIARY (EXPLORATORY) OBJECTIVES: Regarding those participants for which doxorubicin has been released by optimal FUS exposure parameters:
 
 To establish the validity of other minimally-invasive and non-invasive methods of evaluating intratumoural uptake of doxorubicin as an alternative to that used in primary endpoint: 
 a) Fluorescence microscopy of biopsy b) MR-Spectroscopy c) Plasma pharmacokinetics To determine whether the dose of doxorubicin released has a therapeutically significant effect on the target tumour.

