Primary Endpoint:	A demonstrable two-fold increase in, or value exceeding 10µg/g of, the concentration of intra-tumoural doxorubicin at the treated tumour site following FUS-induced mild hyperthermia, in at least 50% of evaluable participants.
Secondary Endpoints:	
 Part I only: Achievement of the desired range of mild hyperthermia in the target tissue as monitored by the implanted thermometry device during FUS exposure

	
 2. Persistence of cell viability stain or percentage of cell or tissue necrosis under 30% following FUS exposure, as assessed by cytological or histological methods 3. Significant bone marrow suppression, deranged liver function and liver toxicity. 4. Adverse events up to 30 days post-intervention: 
 a. Deemed related to ThermoDox® b. Deemed related to FUS
Tertiary (Exploratory) Endpoints:	
Regarding doxorubicin released by optimal FUS exposure parameters:
 
 1. Combined analysis of relevant end points to establish most effective alternative analytical method(s) for quantifying drug release: 
 a. Released biopsy samples exhibiting averaged regions of nuclear or background fluorescence levels at least twice that of a suitable control, as assessed by fluorescence microscopy b. Liver MRI/MR-Spectroscopy indicating targeted delivery of doxorubicin to the tumour by demonstrating a statistically significant increase in the tumour:background ratio of signal intensity following intervention compared to baseline c. A significant decrease of in total doxorubicin plasma levels over time-matched clearance levels, following FUS-induced release 2. Radiological evidence of tumour response at timepoints up to 60 days post-intervention in the FUS-targeted tumour and control(s), as assessed by Principles of Choi and RECIST response evaluation using MRI and CT [11, 12] and SUV_{max} using PET-CT [13]

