¹⁰ During the Ultrasound Session feasibility of intervention is confirmed and a target tumour will be selected by ultrasound. Only one screening ultrasound is required.

¹¹ MRI includes the abdomen. Measurements made using the modified RECIST 1.1 criteria.

¹² Liver MRI includes the abdomen. The first Liver MRI/MR Spectroscopy following intervention can alternatively be performed on the same day as intervention, if intervention is in the morning. It should occur within 36 hours of the completion of intervention, and ideally within 24 hours where possible.

¹³ Liver pCT includes the abdomen. Measurements made using CHOI and the modified RECIST 1.1 criteria.

¹⁴ Three blood samples for pharmacokinetics in both Phases I and II (Pre-Treatment, Unreleased drug, Released drug).

¹⁵ Three biopsies in Part I (Pre-Treatment, Unreleased drug, Released drug), two biopsies in Part II (Released drug).

KEY DEFINITIONS

“Intervention” refers to attempted targeted release of ThermoDox® by mild hyperthermia using a focused ultrasound.

The “FUS-targeted tumour” or “target tumour” refers to the liver tumour treated with FUS following ThermoDox® delivery. This is in contrast to the RECIST definition, which defines target tumours as those measurable lesions which are followed through the patient’s treatment course.

A “non-FUS control tumour” refers to a liver tumour receiving ThermoDox® alone which has been selected for radiological follow-up and comparison with the target tumour.

The “desired range of mild hyperthermia” is used in the context of ThermoDox® release in this study and is defined as achieved bulk tissue temperature in the range of 41-47°C

“Optimal FUS exposure parameters” are defined as those combinations of settings on the HIFU device (power, duty cycle and transducer motion plan) which result in an adequate temperature rise to successfully release doxorubicin from the LTSls in the target tumour, without causing direct thermal tissue damage.

An “evaluable participant” is defined as a participant who has received FUS following delivery of ThermoDox® in Part I or II, and for whom it has been possible to evaluate the outcome of the intervention based on biopsy samples, or radiologically.

An “evaluable sample” is defined as a sample for which sufficient material was available for analysis and the analytical technique has provided quantifiable data.

ABBREVIATIONS

AE	Adverse Event
ADL	Activities of Daily Living
ADR	Adverse Drug Reaction

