To assess the safety of FUS-induced mild hyperthermia for drug delivery	1. Persistence of cell viability stain or percentage of cell or tissue necrosis under 30% following FUS exposure, as assessed by cytological or histological	1. Cytological or histological analysis of biopsy samples processed within 96hr of intervention†

	methods ¹⁶ ‡,§ 2. Adverse events deemed related to FUS up to 30 days post-intervention	2. Adverse event recording for 30 days post-intervention
To assess the local and systemic cytotoxic effects of ThermoDox® in this setting	1. Significant bone marrow suppression, deranged liver function and liver toxicity 2. Adverse events deemed related to ThermoDox® up to 30 days post-intervention	1. Grade 3 and 4 laboratory results from blood tests at Day 1 and Day 15 post intervention 2. Adverse event recording for 30 days post-intervention

Table 2: Secondary Objectives and Endpoints for Parts I & II of the TARDOX Study

Regarding participants for which doxorubicin has been released by optimal FUS exposure parameters:

Tertiary (Exploratory) Objectives	Tertiary (Exploratory) Endpoints	How and when data is captured
1. To establish the validity of other minimally-invasive and non-invasive methods of evaluating intratumoural uptake of doxorubicin as an alternative to that used in primary endpoint	Combined analysis of relevant end points to establish most effective alternative analytical method(s) for quantifying drug release	See below
a. Fluorescence microscopy of biopsy	Released biopsy samples exhibiting regions of nuclear or background fluorescence levels at least twice that of a suitable control, as assessed by fluorescence microscopy ‡,§	Microscopic analysis of biopsy samples processed within 96hr of intervention†
b. MR-Spectroscopy	Liver MRI/MR-Spectroscopy indicating ¹⁷ targeted delivery of doxorubicin to the tumour by demonstrating a statistically significant increase in the tumour:background ratio of signal intensity following intervention compared to baseline	MRI/MR-Spectroscopy signal within 36 hours of intervention
c. Plasma pharmacokinetics	A statistically significant decrease in total doxorubicin plasma levels over time-matched clearance levels, following HIFU-induced release	Analytical chemistry of plasma samples processed within 12hr of intervention†

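### The Table 3 lead-in limits the exploratory method validation to participants with drug release, which conflicts with the all-evaluable rule and, if followed, leaves no participant-level negatives

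*Protocol*

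**What the plan says.** Tertiary objective 1 (Protocol section 3, Table 3) is "To establish the validity of other minimally-invasive and non-invasive methods of evaluating intratumoural uptake of doxorubicin as an alternative to that used in primary endpoint". The candidates are fluorescence microscopy, MR-Spectroscopy and plasma pharmacokinetics.

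The population is set in three places:
- Section 3, lead-in to Table 3: "Regarding participants for which doxorubicin has been released by optimal FUS exposure parameters".
- Synopsis, tertiary objectives: "Regarding those participants for which doxorubicin has been released by optimal FUS exposure parameters".
- Synopsis, tertiary endpoints: "Regarding doxorubicin released by optimal FUS exposure parameters", which refers to drug rather than to participants.

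Key Definitions describes optimal FUS parameters as settings "which result in an adequate temperature rise to successfully release doxorubicin from the LTSls in the target tumour", provided that they cause no direct thermal damage. No section says whether release means the primary-endpoint criterion (a two-fold rise, or more than 10 µg/g).

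Other places point to a wider population. The Study Design entry of the synopsis and section 2 put every evaluable participant of both parts into the endpoint analysis, and section 17.1 says the same of the final analyses. The § qualifier in section 3 requires a result in at least half of the evaluable participants. It is attached to the fluorescence endpoint and to the tumour-response endpoint, both of which stand under the restrictive lead-in.

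**The concern.** Validating a substitute for an assay requires cases in which the assay is negative as well as positive. The lead-in selects on the result that the substitute is meant to detect, and the definition of optimal parameters is itself tied to successful release. Participants who received drug and FUS but had no release are the natural negatives, and they would be dropped.

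This matters most for two of the three methods:
- MR-Spectroscopy is scored as a "statistically significant increase in the tumour:background ratio of signal intensity following intervention compared to baseline". The baseline scan precedes the drug and the next follows FUS, so no scan shows circulating but unreleased drug. The non-FUS control tumour is not biopsied (section 5.4.2) and so has no reference concentration.
- The plasma endpoint is a fall relative to time-matched clearance after FUS, so a pre-FUS sample is not an independent negative for it.

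At stake is whether the trial can say how often an alternative method signals release when there was none.

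**Working it through.** The Protocol gives no figure for the validation objective. Its only relevant number is the maximum of 28 evaluable participants (section 16.1), stated without alpha, power or effect size, so there is no figure to reproduce. Release rates, correlations and test performance below are assumptions. Steps 2 to 5 read release as success on the reference assay.

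**1. The § denominator.** Suppose 14 of 28 release. At least half of evaluable participants means 14 of 28. At least half of those under the lead-in means 7 of 14. The Protocol does not say which sentence governs.

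**2. Agreement when every participant is reference-positive.**
- Specificity = TN / (TN + FP) = 0/0, not estimable.
- Let a share p test positive. Observed agreement is p, and chance agreement is p × 1 + (1 − p) × 0 = p. Kappa = (p − p)/(1 − p) = 0, or 0/0 when p = 1.
- Raw percent agreement equals sensitivity. It is not attenuated, but it says nothing about false positives.

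**3. Correlation on Released samples.** Assume bivariate normality and keep the top share s by concentration. With c = Φ⁻¹(1 − s) and λ = φ(c)/s, the variance ratio is v = 1 + cλ − λ², and

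r′ = ρ√v / √(ρ²v + 1 − ρ²).

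For s = 0.5: c = 0, λ = 0.798, v = 0.363. For ρ = 0.70, r′ = 0.70 × 0.603 / √(0.49 × 0.363 + 0.51) = 0.422/0.830 = 0.51.

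| ρ, all participants | r′, s = 50% | r′, s = 70% | r′, s = 90% |
|---|---|---|---|
| 0.5 | 0.33 | 0.38 | 0.44 |
| 0.7 | 0.51 | 0.57 | 0.64 |
| 0.8 | 0.63 | 0.68 | 0.75 |
| 0.9 | 0.78 | 0.82 | 0.87 |

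**4. What the Unreleased samples recover.** A simulation of 1,000,000 draws assumed 70% release, ρ = 0.8 and Released values 1 SD above Unreleased. Released samples alone give 0.68 after restriction. Pooling each retained participant's Unreleased sample gives 0.84, against 0.83 when all participants are pooled, so the attenuation disappears. This is a favourable case, because it gives everyone an Unreleased sample and only Part I takes that biopsy.

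For sample-level specificity, if all Unreleased samples test negative, the exact 95% lower limit is 0.48 with 5 samples, 0.69 with 10 and 0.77 with 14. Five is the minimum number treated with thermometry before the review that may open Part II (section 2). Part I then stays open, so more are possible.

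**5. What the wider population yields.** With all 28 having paired results and about 80% of non-releasers testing negative:

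| Release rate | Without release | Test-negative | Exact 95% CI, specificity |
|---|---|---|---|
| 50% | 14 | 11 | 0.49–0.95 |
| 60% | 11 | 9 | 0.48–0.98 |
| 70% | 8 | 6 | 0.35–0.97 |
| 80% | 6 | 5 | 0.36–1.00 |
| 90% | 3 | 2 | 0.09–0.99 |

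**The case against.** The best defence is that the lead-in need not be read as an exclusion. The synopsis endpoints speak of released drug, section 5.4.2 labels every post-FUS biopsy Released Drug whatever its assay result, and the general rule covers all evaluable participants. On that reading nobody is removed. This stands as a possible reading, but the Protocol does not choose it, and both the synopsis objectives and Table 3 name participants. The analysis plan, not shown here, may describe the combined analysis. The conflict over the population would still be in the Protocol.

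A reader might infer that specificity cannot be estimated at all, or that a marker positive in everyone would pass as valid. The documents do not support that. Part I takes Pre-Treatment and Unreleased biopsies, and plasma is drawn at three stages in both parts. The endpoints are comparative: fluorescence, for example, requires "Released biopsy samples exhibiting regions of nuclear or background fluorescence levels at least twice that of a suitable control". A signal raised in every sample would fail such a test. These within-participant comparisons are nevertheless few for biopsies, since Part II has no Unreleased biopsy and tissue mass is expected to allow at most one further technique per sample. No section assigns them to the validation.

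Tumour response (objective 2) is different. It asks about the effect of released drug, so conditioning on release is coherent, and non-FUS tumours serve as controls where available. It is not framed as a dose-response analysis.

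**Conclusion.** The point holds as an unreconciled conflict over the analysis population. If the lead-in is followed, and release is equated with success on the reference assay, participant-level specificity and chance-corrected agreement are lost, and correlation on Released samples is attenuated.

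The size of the attenuation is illustrative. It assumes normality, a release rate, and truncation on concentration alone, whereas the primary criterion combines a ratio with an absolute threshold and uses a different comparator in each part. The Protocol also specifies no correlation analysis. It would therefore go too far to say that about half the participants will be discarded, or that agreement in general is attenuated: raw percent agreement is not, and pooling Unreleased samples can remove the effect on correlation.

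The objective is exploratory and the primary conclusion does not change. The correction is worth making because it costs little and makes false positives among treated participants observable.

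**What to change.** - Reword the lead-in to Table 3 and both synopsis entries so that tertiary objectives 1a to 1c are analysed in all evaluable participants with both a Released biopsy concentration and the alternative measure.
- Use the measured concentration as a continuous reference. Report sensitivity and specificity against the primary-endpoint classification, with exact intervals.
- Name the Part I Unreleased samples as additional negatives where tissue mass allows.
- State that the § denominator is all evaluable participants.
- Define release, and keep the released subset as a secondary table.
- For objective 2, report response in all evaluable participants alongside the released subset.

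The cost is a few sentences and a little more analysis. No procedure or sample is added beyond those already scheduled. Fluorescence data will still be limited by tissue mass, and specificity will stay imprecise.

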3 OBJECTIVES AND ENDPOINTS

The objectives and endpoints for the study are detailed in the following tables. Only evaluable samples will be included in endpoint analysis. All endpoints will be evaluated at the end of Phase II.

The following qualifiers (*, †, ‡ and §) apply to Table 1, Table 2 and Table 3:

* In Part II the Unreleased biopsy is not performed and therefore the average value for all evaluable tumours receiving intervention in Part I is used as a comparison for the two-fold increase from Unreleased to Released biopsy.

† Duration refers to the completion of sample processing but not necessarily the sample analysis. The sample may be stored in a fixed or frozen state and analysed at some time period beyond the specified duration, for example to facilitate batch processing.

‡ Analytical method will only be performed where tissue mass allows. It is expected at most one technique can be performed in addition to the primary endpoint for a given sample. Where biopsy mass falls short, the primary endpoint will be prioritised.

§ Must be shown in at least 50% of evaluable participants.

Primary Objective	Primary Endpoint	How and when data is captured
To determine whether targeted release of doxorubicin from ThermoDox® ('drug') using mild hyperthermia generated non-invasively by focused ultrasound (FUS) is feasible in cancer patients	A demonstrable two-fold increase in*, or value exceeding 10µg/g of, the concentration of intra-tumoural doxorubicin at the treated tumour site following FUS-induced mild hyperthermia § Quantification of intra-tumoural drug release will be achieved by direct analysis of the intra-tumoural biopsy samples using standardised curve(s)	Analytical chemistry performed on a recorded mass of biopsy sample processed within 12 hours of intervention†

Table 1: Primary Objective and Endpoints for the TARDOX Study

Secondary Objectives	Secondary Endpoints	How and when data is captured
Part I only: To determine optimal FUS exposure parameters for a range of participant Body Mass Indices (BMIs) and tumour locations within the liver	Achievement of the desired range of mild hyperthermia in the target tissue as monitored by the implanted thermometry device during FUS exposure	Real-time thermometry monitoring during intervention

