2. To determine whether the dose of doxorubicin released has a therapeutically significant effect on the target tumour	Radiological evidence of tumour response at timepoints over 30 up to 60 days in the FUS-targeted tumour and control(s), as assessed by principles of Choi and RECIST response evaluation using MRI and CT [11, 12] and SUV _{max} using PET-CT [13] §	Scans to be performed within 60 days of intervention.

Table 3: Tertiary (Exploratory) Objectives and Endpoints for Parts I & II of the TARDOX Study

¹⁶ In some necrotic tumours, base line necrosis may be high (e.g. >30%) even prior to treatment. Consequently an increase in necrosis by no more than 25% over that of a suitable control can be used as an alternative endpoint.

¹⁷ The spectroscopy signal analysed may not be doxorubicin itself; metabolites or breakdown products of ThermoDox® may be utilized.

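### Table 3 sets out to validate fluorescence, MR-Spectroscopy and plasma PK against the primary assay, but none of its fixed criteria compares a reading with the same participant's measured doxorubicin

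*Protocol*

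**What the plan says.** Protocol section 3, Table 3, gives the first tertiary objective as "To establish the validity of other minimally-invasive and non-invasive methods of evaluating intratumoural uptake of doxorubicin as an alternative to that used in primary endpoint". Its endpoint row reads "Combined analysis of relevant end points to establish most effective alternative analytical method(s) for quantifying drug release". Three method-specific endpoints follow:

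- **a, fluorescence microscopy:** "Released biopsy samples exhibiting regions of nuclear or background fluorescence levels at least twice that of a suitable control". Qualifier § applies: "Must be shown in at least 50% of evaluable participants".
- **b, MR-Spectroscopy:** "demonstrating a statistically significant increase in the tumour:background ratio of signal intensity following intervention compared to baseline". Footnote 17 adds: "The spectroscopy signal analysed may not be doxorubicin itself; metabolites or breakdown products of ThermoDox® may be utilized".
- **c, plasma pharmacokinetics:** "A statistically significant decrease in total doxorubicin plasma levels over time-matched clearance levels, following HIFU-induced release".

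The reference is the primary endpoint in Table 1, a doxorubicin concentration in µg/g from a weighed biopsy. Table 3 is headed as applying to participants in whom drug was released by optimal FUS parameters. Qualifier ‡ in section 3 expects at most one further technique per tissue sample after the primary assay. Section 16.1 caps the trial at 28 evaluable participants. No sample-size, correlation or precision figure is given for this objective.

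**The concern.** To validate a method against a reference, its reading has to be set beside the reference reading in the same participant. Endpoints a to c do not do this. Endpoint a compares fluorescence with a control, b compares the MR ratio with baseline, and c compares plasma doxorubicin with expected clearance. Each can show that a signal moved. None shows that a larger signal goes with more drug in the tumour, which is what a substitute for a quantitative assay needs.

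The error can run both ways. A method with a strong but uninformative signal meets its criterion. A method that follows concentration closely but gives a modest signal fails it. Footnote 17 makes the comparison more important for MR, since the signal may not come from doxorubicin. At stake is whether the trial can say which less invasive measure could stand in for the biopsy assay, although it collects the readings needed to answer.

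**Working it through.** The plan states no figure for this objective, so there is none to reproduce. The checks below use assumed values, marked as such.

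**1. Criteria set beside the objective.** The objective names the primary assay as comparator. The comparators in a, b and c are a control sample, baseline and time-matched clearance. Section 12 adds only a comparison of Unreleased with Released biopsies. The participant's own concentration appears in none of the three criteria.

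**2. Chance that an uninformative method meets rule a.** If each participant exceeds twice control with probability p, whatever the concentration, then

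P(pass) = P(X ≥ n/2), X ~ Binomial(n, p).

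| n | p = 0.4 | p = 0.5 | p = 0.6 |
|---|---|---|---|
| 14 | 0.308 | 0.605 | 0.850 |
| 20 | 0.245 | 0.588 | 0.872 |
| 28 | 0.187 | 0.575 | 0.898 |

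The values of p and the two smaller n are assumptions; 28 is the protocol's maximum.

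**3. Does the rule respond to tracking?** Assume log fold reading = log(m) + 0.5·[ρL + √(1−ρ²)·e], where m is the median fold reading, L the standardised log concentration, e independent standard normal noise, and 0.5 an assumed SD. The bracket has variance 1 for every ρ, so the chance of exceeding two-fold is Φ[(log m − log 2)/0.5], which does not contain ρ.

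- m = 2.5: Φ(0.446) = 0.67. The chance of at least 14 of 28 is 0.98.
- m = 1.5: Φ(−0.575) = 0.28. The chance of at least 14 of 28 is 0.012.

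Simulation at ρ = 0, 0.5 and 0.9 agrees: about 98% of trials pass at m = 2.5 and about 1% at m = 1.5, at every ρ. That the rule ignores ρ follows from its form; only the levels depend on the assumptions.

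**4. What a paired analysis can do.** In the same model at n = 28, a one-sided 2.5% test of the paired Pearson correlation is significant in about 2.5% of trials at ρ = 0, about 79% at ρ = 0.5 and essentially all at ρ = 0.9. The approximate 95% interval is tanh[atanh(r) ± 1.96/√(n−3)]. For r = 0.8:

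- n = 28: 0.61 to 0.90
- n = 20: 0.55 to 0.92
- n = 10: 0.34 to 0.95

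These are Fisher-z intervals for a Pearson correlation; Spearman intervals are somewhat wider.

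**5. Effect of the released-only heading.** Assume a correlation of 0.6, bivariate-normal log readings, 28 evaluable participants, and release in the 50% to 65% with the highest concentrations. Simulated power of a two-sided 5% Spearman test is about 0.9 in all 28, and about 0.3 (50% released) to 0.4 (65% released) in the released subset. Fewer pairs and a narrower concentration range both contribute.

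**The case against.** The strongest reply is that an undefined analysis is being treated as a wrong one. The endpoint proper is the combined-analysis row, which speaks of relevant endpoints without limiting them to a to c, and the objective itself names the primary assay. Sections 17 and 17.5 defer analysis detail to a statistical analysis plan that is not at hand. A reader might infer that the protocol rules pairing out, or that a method meeting its criterion will be declared valid. The text says neither; pairing is unstated, not excluded. What remains is that the three criteria the protocol does fix are endpoints, not analysis detail, and they do not bear on validity.

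Three further limits stand:

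- A reader might picture fluorescence positive in one half of participants and the assay high in the other half, with both passing. The heading of Table 3 restricts the set to participants with release. If release is judged by the primary assay, low-assay participants are excluded and the example fails. Concentration can still vary within that set, so the criteria remain uninformative about tracking.
- A reader might attach a power loss to comparing two yes/no classifications. The protocol names no such test, so no such loss can be charged to it.
- Whether significance in b and c is judged per participant or across the group is not stated. Neither reading brings in the assay.

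Tissue and timing limits are also real. Viability or necrosis assessment competes with microscopy under qualifier ‡. MR may be read up to 36 hours after intervention. FUS may finish at any point up to 4 hours after infusion start (section 8.4), so a raw plasma level would be mixed up with sampling time.

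**Conclusion.** The point holds in limited form. The criteria fixed in Table 3 cannot show that a method is a valid alternative to the primary assay, because whether they are met depends on signal size and not on agreement with measured concentration. For fluorescence, an uninformative reading with an assumed 60% positivity meets the rule with probability 0.85 to 0.90 at 14 to 28 participants. A closely tracking reading with an assumed median 1.5-fold signal and log SD 0.5 meets it about 1% of the time at 28. No comparable figure is given for b and c, where the argument rests on their wording.

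The conclusion does not depend on the assumed values; the probabilities do. The objective is exploratory, so no primary, secondary or safety conclusion changes. The paired readings are largely collected anyway, so the defect can be corrected before analysis.

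**What to change.** Restate the validity endpoint for tertiary objective 1 as the association, across participants, of each continuous reading with the same participant's log Released-biopsy concentration, reported as a Spearman correlation with 95% CI. The readings would be:

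- the fluorescence level;
- the change from baseline in MR tumour:background ratio;
- the deviation of plasma doxorubicin from its time-matched clearance value, not the raw level.

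Compare the methods on these estimates and keep a to c as descriptive summaries. Run the analysis in all evaluable participants with paired data, not only those with release. Left in the released-only set, it would lose most of its power under the assumptions above.

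The cost is a change of wording in the protocol and statistical analysis plan, and a small amount of analysis, with no added samples, scans or participants. Qualifier ‡ will reduce the microscopy pairs, MR is read later and may reflect metabolites, and intervals will be wide. The number of pairs should be reported with each estimate.
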